9.2.1. Rating the Severity of Adverse Events

All AEs will be assessed for severity by the PI or designee using the FDA Guidance for Industry: *Toxicity Grading Scale for Healthy Adult and Adolescent Volunteers Enrolled in Preventive Vaccine Clinical Trials* {[CBER](#), 2007 (refer to [Appendix A](#))}.

The toxicity grading scale has specific grading options for some clinical symptoms, such as nausea/vomiting, diarrhea, headache, fatigue, and myalgia. Any AEs not specifically identified in the Toxicity Grading Scale will use the scale identified for systemic (general) illness or clinical AE. For AEs being reporting from clinical assessments, the PI or designee will refer to the specific sections on clinical laboratory tests([Section 8.3.2](#)), PEs ([Section 8.3.3](#)), vital signs ([Section 8.3.4](#)), and e-diary reactogenicity ([Section 8.3.5.1](#)) on how and when to report AEs and AE severity in applying the toxicity grading scale.

9.2.2. Rating the Causality of Adverse Events

The PI's (or designee's) assessment of an AE's causal relationship to the IP will be documented on the AE eCRF. This causality assessment will be performed only by those study personnel listed on the Delegation of Authority Log as having both the authority and medical training to make such a determination. The following guidelines are provided for this assessment.

1. Unrelated: there is no relationship between either the vaccine or the antibiotic and the reported event.
2. Possibly related to antibiotic (Groups 1 and 2): the event follows a reasonable temporal sequence from the time of antibiotic administration and/or follows a known response pattern to the antibiotic, but could also have been produced by other factors.
3. Possibly related to AV7909 (Groups 1 through 3): the event follows a reasonable temporal sequence from the time of vaccine administration and/or follows a known response pattern to the vaccine, but could also have been produced by other factors.

AV7909 Anthrax Vaccine

IND 014451

Protocol EBS.AVA.210, Version 3.0 (28 October 2019)

4. Probably related to antibiotic (Groups 1 and 2): a reasonable temporal sequence of the event with antibiotic administration exists and, based upon the known pharmacological action(s) of the antibiotic, known or previously reported adverse reactions to the antibiotic or class to which the antibiotic belongs (for ciprofloxacin this would be fluoroquinolones and for doxycycline this would be tetracyclines), or the Investigator's clinical judgment, the association of the event with the antibiotic seems likely.
5. Probably related to AV7909 (Groups 1 through 3): a reasonable temporal sequence of the event with vaccine administration exists and, based upon the known action of the vaccine, known or previously reported adverse reactions to the vaccine, or the Investigator's clinical judgment, the association of the event with the vaccine seems likely.
6. Definitely related to antibiotic (Groups 1 and 2): a definite causal relationship exists between antibiotic administration and the AE, and other conditions (eg, concurrent illness, progression/expression of disease state or concurrent medication reaction) do not appear to explain the event.
7. Definitely related to AV7909 (Groups 1 through 3): a definite causal relationship exists between vaccine administration and the AE, and other conditions (eg, concurrent illness, progression/expression of disease state or concurrent medication reaction) do not appear to explain the event.

If the relationship between the AE and the IP is determined to be "possible" or "probable" or "definitely related," the event will be considered to be related to the IP.

9.2.3. Eliciting Adverse Events from Other Safety Assessments

Clinical observations during safety evaluations (ie, PEs, vital signs, clinical laboratory tests) determined by the PI or designee to be abnormal and to represent a clinically significant change from baseline must be reported on the AE eCRF regardless of causal association with the IP. This includes any new observation presenting after the dose of IP (either antibiotic or AV7909) or deterioration of baseline condition (ie, increased severity/frequency) after the first vaccination through Day 51 or EWV. If there is any doubt as to whether a clinical observation is an AE, the event will be considered an AE and recorded on the AE eCRF. Additionally, certain types of observations must be reported by the PI or designee as AEs, as follows (refer to the listed sections below for details on retesting and repeat testing requirements associated with this reporting where applicable):

- Following the dose of any IP, all Grade 3 or higher clinical laboratory abnormalities (sample retested and, if needed, test repeated), unless covered under a disease or syndrome that is already reported as an AE; refer to [Section 8.3.2](#) for details.
- Following the first dose of any IP, all vital sign abnormalities found to be Grade 3 or higher in two out of three assessments (original plus two repeats); refer to [Section 8.3.4](#) for details.

Additionally, while reactogenicity from the e-diary will not be duplicated in AE reporting, the PI or designee will record as AEs any e-diary reactogenicity that is serious, results in

AV7909 Anthrax Vaccine
IND 014451
Protocol EBS.AVA.210, Version 3.0 (28 October 2019)

discontinuation of IP or withdrawal from the study, or remains unresolved as of Day 51/EWV (refer to [Section 8.3.5.1](#)).

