3.2.2. Secondary Endpoints

Safety

- Incidence of AEs from the first dose of any IP through the Final Study Visit (Day 51 ± 1 d)
- Incidence of serious AEs (SAEs) from the first dose of any IP until the 12-month follow-up (Day 388 ± 14 d)
- Incidence of solicited systemic and injection site reactions reported in participant e-diaries following each vaccination
- Incidence of AESIs from the first dose of any IP until the 12-month follow-up (Day 388 ± 14 d)
- Incidence of clinical laboratory abnormalities

Pharmacokinetics and Immunogenicity

- AUC_{0-12h} and C_{max} for ciprofloxacin on Days 4 and 31 and for doxycycline on Days 2 and 32
- Geometric mean TNA 50% neutralizing factor (NF_{50}) values 2 weeks after the second vaccination (Day 37 ± 1 d)

AV7909 Anthrax Vaccine

IND 014451

Protocol EBS.AVA.210, Version 3.0 (28 October 2019)

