8.3.3. Physical Examination

Complete PEs will be performed at screening, the Final Study Visit (Day 51) and early withdrawal, if applicable. The following will be examined: cardiovascular system (including a standard 12-lead electrocardiogram at screening only, to be read at the site); lymphatic/hematological, respiratory system; nervous system; skin and appendages; abdominal/gastrointestinal system; metabolic/endocrine, musculoskeletal system; and ear, nose, and throat.

Symptom-directed PEs will be performed at all visits except the Screening, Final Study Visits and early withdrawal (including any unscheduled visits), only if required (ie, in response to the report/collection of AEs/SAEs/potential AESIs).

Abnormal PE findings are to be recorded as AEs if new or changed in severity any time after the first administration of any IP and PE AEs should be assessed for severity and causality. Grade 3 (or higher) PE findings could trigger individual or study halting rules if considered associated with IP administration (see [Section 7](#)). Physical examination abnormalities are not separately reported as AEs if the PE abnormality is part of a symptom complex that is already reported as an AE.

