9.2. Eliciting and Reporting Adverse Events

AEs (including SAEs and potential AESIs) reported spontaneously by the participant and/or in response to an open question from the PI or designee or revealed by observation (eg, during PE

AV7909 Anthrax Vaccine

IND 014451

Protocol EBS.AVA.210, Version 3.0 (28 October 2019)

or from a clinical test result) will be recorded on the AE eCRF if they occurred from the time of the first administration of any IP (Day 2 for Group 2, Day 4 for Groups 1 or Day 8 for Group 3) through Day 51 or EWV, regardless of causal association with the IP. AE reporting is required for any new observation presenting after the first receipt of any IP or for a deterioration of baseline condition (eg, increased severity/frequency). From the signing of the ICF until immediately before the administration of their first IP, only AEs resulting from a study-related procedure will be recorded on the AE eCRF; all other events reported in these time periods will be recorded as signs and symptoms on the Medical History eCRF. If there is any doubt as to whether a clinical or laboratory observation is an AE, the event will be considered an AE and recorded on the AE eCRF. After Day 51 and through the 12-month safety follow-up, AEs, SAEs (meeting definition per [Section 9.1.2](#)) and AEs assessed by the DSMB to be of autoimmune etiology (refer to [Section 8.5](#)), ie, AESIs, will be recorded on the AE eCRF.

Refer to the specific sections on clinical laboratory tests ([Section 8.3.2](#)), PEs ([Section 8.3.3](#)), vital signs ([Section 8.3.4](#)), and e-diary reactogenicity ([Section 8.3.5.1](#)) for details on AE reporting based on participant observation and clinical test results.

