### 8.1.3 Drug/Vaccine Related TEAEs

Adverse event causal relationship to the study treatment will be assessed by the PI or designee using terms and scales “Unrelated”, “Possibly related”, “Probably related”, and “Definitely related”. If the relationship between the AE and the study treatment is determined to be “Possibly” or “Probably” or “Definitely related”, the event will be considered as related to the IP.

To assess the causality between AEs and the study treatment ciprofloxacin, doxycycline, and AV7909, TEAEs will be tabulated with the structures as follows:

- TEAEs by SOC, PT, and Relationship to Study Vaccine.
- TEAEs by SOC, PT, and Relationship to Antibiotics.
- TEAEs onset prior to the first vaccination by SOC, PT, and relationship to ciprofloxacin or Doxycycline.

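### Protocol Section 9.2.3 dates worsening of a baseline condition from first vaccination, while the other AE rules start at first IP, so worsening on antibiotic alone may be recorded or dated inconsistently

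*Protocol*

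**What the plan says.** Protocol Section 9.2.3 covers findings from physical examinations, vital signs and laboratory tests. Its lead sentence sends to the AE form any abnormal finding that the investigator judges a clinically significant change from baseline. The next sentence says what this includes and gives two start points. For new findings it is "any new observation presenting after the dose of IP (either antibiotic or AV7909". For worsening it is "deterioration of baseline condition (ie, increased severity/frequency) after the first vaccination through Day 51 or EWV".

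Elsewhere the start is the first dose of any IP:

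- Section 9.2: "AE reporting is required for any new observation presenting after the first receipt of any IP or for a deterioration of baseline condition". It gives the start as Day 2 for Group 2, Day 4 for Group 1 and Day 8 for Group 3.
- Section 8.3.3: "Abnormal PE findings are to be recorded as AEs if new or changed in severity any time after the first administration of any IP".
- Section 3.2.2, secondary safety endpoint: "Incidence of AEs from the first dose of any IP through the Final Study Visit".
- Protocol Section 10.6.1 and SAP Section 8.1.1: a TEAE includes a pre-existing event that worsens after treatment begins.

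SAP Section 8.1.3 plans a table of "TEAEs onset prior to the first vaccination by SOC, PT, and relationship to ciprofloxacin or Doxycycline".

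**The concern.** In Groups 1 and 2 the time from first antibiotic dose to vaccination 1 is the only period on antibiotic before any vaccine, and the SAP gives it its own table. A site that works from the worsening clause in 9.2.3 alone could treat that period as outside the window for a pre-existing finding that gets worse. It might then leave the event off the AE form, or record it only once it persists past vaccination and date the onset there. Either error would lower the antibiotic-only counts. Group 3 cannot be affected, because its first IP is the vaccine and the two start points coincide.

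**Working it through.** The plan states no figure on this point. The check is a comparison of texts and a count of days.

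**1. Start points side by side**

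| Rule | Start for worsening |
|---|---|
| 9.2.3, worsening clause | First vaccination (Day 8) |
| 9.2.3, lead sentence | Change from baseline; no vaccination condition |
| 9.2 | First IP (Day 2 or Day 4 in the antibiotic groups) |
| 8.3.3 (examinations) | First IP |
| 8.3.2 (laboratory), 8.3.4 (vital signs) | Clinically significant change from baseline; no vaccination condition |
| AE endpoint and TEAE definition | First IP or start of treatment |

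Only the worsening clause uses vaccination.

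**2. Length of the window where the anchors differ**

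Reporting days = 51 − first IP day + 1. Full days before vaccination = 8 − first IP day.

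- Group 1: 51 − 4 + 1 = 48 and 8 − 4 = 4, so 4/48 = 8.3%.
- Group 2: 51 − 2 + 1 = 50 and 8 − 2 = 6, so 6/50 = 12%.

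Groups 1A and 2A are vaccinated in the evening of Day 8 (Section 6.1.4). Counting Day 8 as well gives upper values of 5/48 = 10.4% and 7/50 = 14%.

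Doses taken before vaccination 1, at two a day:

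- 1A: 4 × 2 + 2 = 10
- 1B: 4 × 2 + 1 = 9
- 2A: 6 × 2 + 2 = 14
- 2B: 6 × 2 + 1 = 13

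The same schedule gives 12 + 6 + 13 = 31 ciprofloxacin and 16 + 6 + 13 = 35 doxycycline doses, which match the totals in Sections 6.1.5 and 6.1.6. About 70 + 70 = 140 of 210 participants have such a window.

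**3. What can be found in the window**

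- Vital signs: all four antibiotic subgroups are checked before vaccination on Day 8 (8.1.2.5, 8.1.3.2, 8.1.4.5, 8.1.5.2). The Day 4 check in 1A and the Day 2 check in 2A are listed ahead of the first dose (8.1.2.2, 8.1.4.2), so they add little.
- Examinations: symptom-directed only, when required.
- Safety laboratory tests: Screening, Day 51 or early withdrawal (8.3.2). None is scheduled between first antibiotic and vaccination 1.
- Early withdrawal: a Group 1 or 2 participant withdrawn before vaccination 1 (6.1.4) is asked to return for an examination, vital signs and laboratory tests (8.1.8). This person is in the Safety Population (10.3), yet the 9.2.3 worsening clause never starts for them.

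**4. What other rules already secure**

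- Symptoms reported by participants fall under 9.2.
- Grade 3 or higher laboratory and vital-sign abnormalities are reportable after IP dosing under 9.2.3 itself.
- What remains exposed to inconsistent handling is mainly sub-Grade 3 examination or vital-sign worsening, plus early-withdrawal findings in the never-vaccinated.

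**5. Route to the analysis**

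SAP 8.1.3 selects on onset before first vaccination. An event dated after vaccination 1 would still be a TEAE under SAP 8.1.1 but would drop out of that table. An unrecorded event would drop out of every table.

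**The case against.** The strongest reply is that nothing is lost if the protocol is read as a whole.

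- The clause sits in a sentence that illustrates what the lead sentence includes. It does not say that only post-vaccination worsening counts, and the lead sentence already covers any clinically significant change from baseline.
- Section 9.2 separately requires recording from first IP, and it names findings from examinations and tests.
- Sections 9.2 and 9.2.1 send sites to 8.3.2, 8.3.3, 8.3.4 and 8.3.5.1 for the reporting rules on assessments. Those for laboratory tests, examinations and vital signs do not start at vaccination.
- The Day 8 procedures in every antibiotic subgroup have AEs recorded before vaccination, and the early withdrawal visit also records AEs.
- Section 9.2.3 tells sites to record an event when in doubt.

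All of this stands. A reader might infer that pre-vaccination worsening is not reportable under 9.2.3, or that 9.2.3 overrides 9.2 as the more specific text. The documents support neither inference.

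The reply does not make the two start points in one sentence agree. The doubt rule concerns whether an observation is an AE, and it does not correct a stated date. A site working from that sentence can still go wrong.

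**Conclusion.** The wording in 9.2.3 is inconsistent with the rest of the AE rules and should be aligned. It is a minor point. The consequence is a risk of uneven recording or late onset dating in Groups 1 and 2, confined mainly to sub-Grade 3 examination or vital-sign worsening on antibiotic alone and to early-withdrawal findings in participants never vaccinated. The table it could affect is the pre-vaccination TEAE table in SAP 8.1.3. New findings and participant-reported symptoms still enter that table.

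It is tempting to read the 8.3% and 12% as the share of worsening AEs that would be missed. They are shares of calendar reporting days. Turning them into events would need a constant event rate and sites that follow only the one clause, and the documents support neither assumption. They give no rate for such findings, so the number of events cannot be estimated. Endpoint definitions, the TEAE rule, sample size and power are unaffected.

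**What to change.** In Protocol Section 9.2.3, start the worsening clause at the first dose of any IP instead of the first vaccination, and leave its end point (Day 51 or EWV) as it is. Send sites a short clarification that worsening first seen on antibiotic before vaccination 1 is recorded with its true onset date, including in participants withdrawn before vaccination. The cost is one phrase and one notice. No assessment is added and the SAP needs no change.

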9.3. Immediately Reportable Events

9.3.1. Principal Investigator's Responsibilities

The following events must be reported via email immediately (ie, within 24 hours of awareness), by the site PI or designee to [REDACTED]:

- Any SAE regardless of causal association with any IP
- Any potential AESI, ie, AE of autoimmune etiology (refer to the list of AESI terms in [Appendix B](#)) regardless of causal association with any IP (ie, ciprofloxacin, doxycycline or AV7909)
- Any pregnancy where conception occurred after first exposure to any IP (ie, ciprofloxacin, doxycycline or AV7909) and prior to 12 months after last receipt of either IP

The appropriate form (listed below) will be completed and sent by email to the following address:

[REDACTED]
[REDACTED]
[REDACTED]
[REDACTED]

For SAEs and AESIs, the Serious Adverse Event and/or Adverse Event of Special Interest Report Form will be completed (abbreviated hereafter SAE Report Form, AESI Report Form). Note that the SAE and AESI Report Form are not the same as the AE eCRF. Accompanying these forms will be source documentation or medical records (eg, discharge summary for hospitalizations, lab reports) which support a diagnosis. Participant identifiers (eg, individual's name, address, telephone number, social security number, medical record number, or hospital/laboratory number) must be redacted from the source documentation.

All SAEs that are unexpected (eg, adverse drug reactions) must be reported to the IRB/IEC as required by ICH GCP E6.

Confirmed pregnancies where conception occurred after first exposure to any IP, and prior to 12 months after last receipt of any IP will be reported to Global PV using the Pregnancy Notification Form. Although normal pregnancy is not an AE, it will mandate discontinuation of IP (refer to [Section 9.4](#)).

9.3.2. Sponsor's Reporting Requirements

A SUSAR is a suspected adverse reaction that is both serious and unexpected. As specified in 21 CFR 312.32, SUSARs will be reported by the Sponsor of the Investigational New Drug Application (IND) to the FDA and to all participating PIs in an IND safety report as soon as possible, no later than 15 calendar days after the Sponsor becomes aware of the suspected adverse reaction (21 CFR 312.32(c)(1)).

[REDACTED]

AV7909 Anthrax Vaccine
IND 014451
Protocol EBS.AVA.210, Version 3.0 (28 October 2019)

In addition, any unexpected fatal or life-threatening suspected adverse reaction will be reported to FDA no later than seven calendar days after Emergent's initial receipt of the information (21 CFR 312.32(c)(2)).

The Sponsor will report AESIs to FDA within 15 calendar days after becoming aware of the AESI.

9.4. Pregnancy

Prior to trial enrollment, female participants must be advised of the importance of avoiding pregnancy during trial participation and the risks of an unintentional pregnancy. The participant must sign an ICF stating that the risk factors and consequences were communicated.

To be eligible to enroll in the study, any female participant must certify either that she is surgically sterile (ie, had a hysterectomy, bilateral oophorectomy or bilateral salpingectomy), postmenopausal (defined as >12 consecutive months without menses and Screening FSH >30 mIU/mL) or has been using an effective method of birth control for at least one month prior to Day 1. Methods of acceptable birth control are listed in [Section 5.1](#). Additionally, WOCBP randomized to Groups 1 and 2 must be willing to add a double barrier method of birth control if they are not surgically sterile or postmenopausal, and their primary method of birth control is hormonal or an IUD.

All women will have a serum pregnancy test performed at screening and at the EWV, if applicable, unless they are postmenopausal (confirmed with FSH >30 mIU/mL at screening) or indicate that they are surgically sterile. All WOCBP will also receive a UPT within 24 hours prior to each AV7909 vaccination. Vaccinations will not be administered to participants who test positive for pregnancy.

In addition, a UPT will be performed on the Day 51 for WOCBP participants in all groups. Positive UPTs will be confirmed with a serum pregnancy test. Pregnancy is not considered an AE in this study. If a participant's pregnancy is detected between Randomization and Day 2, no IP is to be administered and the participant is to be withdrawn from the study.

If a participant becomes pregnant at any time after Day 2, (ie, after receipt of at least one dose of either IP), and where conception occurs prior to 12 months after last receipt of either IP, the pregnancy is to be reported within 24 hours of awareness by completing the Pregnancy Notification Form and forwarding it to the Global Pharmacovigilance Department (see [Section 9.3.1](#)). No further IP will be administered to the participant. Participants will also be encouraged to continue planned safety follow-up in the study.

All pregnancies occurring after Day 2 (ie, after receipt of at least one dose of either IP), and where conception occurs prior to 12 months after last receipt of either IP are to be followed to outcome (eg, delivery, spontaneous abortion, or therapeutic abortion), including after the study is completed. When the PI becomes aware of the outcome of the pregnancy, a Pregnancy Outcome Form will be completed and forwarded to the Global Pharmacovigilance Department by email (see [Section 9.3.1](#)) within 24 hours of awareness. A pregnancy outcome of spontaneous miscarriage, congenital anomaly or birth defect is considered an SAE and must be reported according to the procedures described in [Section 9.3.1](#) above. As applicable, contact will be made when the infant is ~28 days old for a final follow-up.

9.5. Reporting of Other Information – Unanticipated Problems

As outlined by the Office for Human Research Protection (OHRP), unanticipated problems must be reported to the IRB according to the requirements of 45 CFR Part 46. Unanticipated problems are considered to include any incident, experience, or outcome that meets ALL of the following criteria:

- Unexpected (in terms of nature, severity, or frequency) given:
 - Procedures that are described in the study-related documents, such as the IRB approved research protocol and informed consent document.
 - The characteristics of the participant population being entered into the study.
- Related or possibly related to participation in the study which means there is a reasonable possibility that the incident, experience, or outcome may have been caused by the sample collection.
- Suggests that the study places participants or others at a greater risk of harm (including physical, psychological, economic, or social harm) than was previously known or recognized.

An incidence, experience, or outcome that meets the three criteria above generally will warrant consideration of substantive changes in the study or informed consent process/document or other corrective actions in order to protect the safety, welfare, or rights of participants or others. Only a small subset of AEs occurring in human subjects participating in a clinical study will meet these three criteria for an unanticipated problem. There are other types of incidents, experiences, and outcomes that occur during the conduct of clinical study that represent unanticipated problems but are not considered AEs. For example, some unanticipated problems involve social or economic harm instead of the physical or psychological harm associated with AEs. In other cases, unanticipated problems place participants or others at increased risk of harm, but no harm occurs.

The investigator should promptly notify the IRB when an unanticipated problem involving risks to participants or others is identified. Also, the investigator should notify Emergent and CRO of unanticipated problem(s).

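### Read literally, Protocol Section 9.5 leaves problems caused by AV7909, ciprofloxacin or doxycycline outside its definition of an unanticipated problem, a narrow but real gap in prompt notice to the IRB

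*Protocol*

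**What the plan says.** Protocol Section 9.5 makes the definition conjunctive: "Unanticipated problems are considered to include any incident, experience, or outcome that meets ALL of the following criteria". In outline, the criteria are that the event is unexpected, that it is related to the study, and that it suggests greater risk than was known before. The second opens broadly, "Related or possibly related to participation in the study which means there is a reasonable possibility", and the definition it gives names one cause only: "there is a reasonable possibility that the incident, experience, or outcome may have been caused by the sample collection". The section then tells the investigator to notify the IRB promptly of such a problem and to tell the sponsor and the CRO.

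Section 9.3.1 gives a separate route for one class of event: "All SAEs that are unexpected (eg, adverse drug reactions) must be reported to the IRB/IEC as required by ICH GCP E6".

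**The concern.** This is an interventional trial. Every participant is to receive two doses of AV7909, and Groups 1 and 2 also take ciprofloxacin or doxycycline. The products are an obvious possible source of an unexpected problem, yet the relatedness test in Section 9.5 does not mention them.

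The rule decides whether the IRB is told. Section 9.5 itself says that a qualifying problem will generally call for considering substantive changes to the study or to the consent process. If a site applies criterion 2 as written, a product-related problem that is neither serious nor a potential AESI has no stated prompt route from investigator to IRB, even when it is unexpected and points to higher risk.

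**Working it through.** No arithmetic applies. The check is whether the wording excludes the products, whether other text restores them, and which events then lack a route to the IRB.

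**1. Are the criteria joint?** Yes. The section requires all of them and later refers again to "An incidence, experience, or outcome that meets the three criteria above".

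**2. Is sample collection a definition or an example?** It follows the words *which means*, so it defines. Nothing marks it as one cause among several.

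**3. Does other text widen the term?** No other section of the protocol or SAP defines an unanticipated problem.

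**4. Is the wording consistent with the rest of the protocol?** It conflicts in three places.
- Within criterion 2, participation in this study includes receiving the products, which is wider than giving samples.
- Section 9.2.2 builds its whole causality scale, from unrelated to definitely related, on the vaccine and the antibiotic.
- Section 9.5 expects some AEs to qualify and allows for problems that raise risk without harm. Product-related events are natural candidates for both, and the literal test removes them.

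**5. Which product-related events are caught by another route?**

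| Event | Other route in the protocol | Does it reach the IRB? |
|---|---|---|
| Unexpected SAE | 9.3.1 | Yes |
| Potential AESI, serious or not | 9.3.1, to the sponsor within 24 hours; 9.3.2, AESIs to FDA; 12.1, monitors check IRB submission | Yes, where reporting criteria are met |
| Severe but non-serious AE | 8.5, DSMB Chair; 7.1, possible study halt | Not stated |
| Other non-serious AE through Day 51 | 9.2, AE eCRF regardless of cause; 11.3 and 12.1, sponsor and CRO data review | Not stated |
| Temperature excursion or defective vial | 6.2.5 and 6.2.2, to the CRO | Not stated |
| Protocol deviation | 11.6 | Yes, under each IRB's requirements |
| Risk that leads to a protocol change | 14 | Yes, but only once a change is made |

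**6. What remains?** The rows without a stated IRB route share one feature: the sponsor, CRO or DSMB is informed and the IRB is not named. Deviations and amendments do not close this, because a product risk can emerge with full adherence and before any amendment. Two kinds of event are left for Section 9.5 alone:
- a non-serious, non-AESI, unexpected product-related harm that suggests greater risk;
- a newly recognised product risk with no harm yet.

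**The case against.** The best defence is that the clause should be read in context. Section 9.5 opens by tying reporting to 45 CFR Part 46. It introduces the criteria as what such problems are considered to include. It leads criterion 2 with study participation, and it goes on to discuss AEs, social and economic harm, and risk to people other than participants. All of this points to a wider intent than harm from blood or urine sampling, and a careful investigator might well report a product-related problem anyway.

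Much of that stands. The wider intent is plausible, and the fault is best described as an inconsistency inside criterion 2 that works against the purpose of its own section. It does not rescue the text. The defining words are explicit, the criteria are joint, and the documents do not reproduce the regulation's own definition for a site to fall back on. A reporting rule for up to five sites should not depend on staff setting aside its stated definition.

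A reader might go further and infer that harms caused by the products would go unreported, or that the sponsor and CRO would not hear of them. The documents do not support that. Unexpected SAEs have their own IRB route, potential AESIs are handled separately, and the sponsor, CRO or DSMB receives most of the rest.

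**Conclusion.** The wording of criterion 2 is wrong for this trial and should be corrected. This is more than a clerical matter, because the sentence is an operative safety-reporting rule. Its consequence is limited to the two kinds of event left at the end of the check, and for those the loss is chiefly prompt notice to the IRB.

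The conclusion assumes that sites apply Section 9.5 as written and that no local IRB rule fills the gap; the documents do not describe local rules. The effect cannot be given as a number. A reader might be tempted to count planned vaccinations and antibiotic doses, but those counts describe exposure, not missed reports, and Section 9.5 itself expects few AEs to qualify. A reader might also infer that the phrase was carried over from a study that only collected specimens. Nothing in the documents shows where it came from, and the point does not need it.

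No endpoint, sample size or analysis is touched.

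**What to change.** In Protocol Section 9.5, criterion 2, replace the closing reference to sample collection with: *caused by the investigational products (AV7909, ciprofloxacin or doxycycline) or the procedures involved in the research*. Sample collection stays covered as a research procedure. Leave the other two criteria unchanged.

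This is one phrase in the next amendment. It alters no dose, schedule or clinical rule. The downside is possibly a few more IRB notifications.
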